### **D. Rejection criteria**

- (1) Patients who violate the requirements of the test protocol
- (2) Patients with poor-recording, incomplete, or inaccurate data

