### **III. Research Design**

1. This study is a prospective, nonrandomized, open-label, single-arm clinical trial. The sirolimus capsule (Rapamycin, Yixinke®), 0.5 mg/grain\*20/box, is produced by North China Pharmaceutical Co., Ltd.
2. All patients who meet inclusion criteria and sign informed consents receive sirolimus treatment for at least 6 months. Patients are followed up in a regular schedule.
3. No less than 20 patients should be enrolled.

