### **C. Exit criteria**

- (1) An allergic reaction occurs.
- (2) The patient requests withdrawal: at his or her own discretion or at the request of his or her legal representative. Subjects may refuse to participate in further studies at any time without providing reasons. Subjects will not be affected because of such decision.
- (3) Subjects are required to withdraw from the study in certain special circumstances (eg, there is significant issues of compliance, safety, or surgery for venous malformations)
- (4) Other situations in which the study must be terminated. For example, the investigators believe that continuing the study may be harmful to the health of subjects.

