### **C. Adults' dosage regimen**

Oral administration

1) Initial dose and dosing schedule: sirolimus 2mg, once a day. Maintain drug trough concentration of 5-10ng / mL in blood. If adverse events are too severe to tolerate, daily dosage can be reduced by 0.5mg every week. The minimum dosage is 1 mg/day. If patient still cannot tolerate minimum dosage, withdraw from the study. If patient could tolerate the possible adverse events, continue to take the original dose for 3 months, and evaluate improvement of disease condition.

2) Subsequent dose and dosing schedule: After taking sirolimus 2 mg once a day for 3 months, those with improved condition continue to take the original dose. If improvement of disease condition is not obvious, change dosage to 2.5mg-3mg once a day. If this dosage cannot be tolerated, patients may withdraw from the study. If it can be tolerated, continue to take for another 3 months and reassess the improvement of condition.

3) Blood drug concentration test: Blood samples are taken at 1st, 3rd and 6th months of dosage schedule.

4) Iron supplementation: For subjects with hemoglobin  $\leq$  10.9 g / dl, iron supplementation should be provided according to the standard dosing regimen, but iron supplementation is

not considered as study treatment and will be recorded as concomitant medication.

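### The rejection rule in IV.D has no threshold and section VIII names no analysis set, so treated patients can be removed from an uncontrolled before-after summary; the size of any bias is unknown, but the documented routes lean favourable to sirolimus

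*Combined protocol and SAP*

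**What the plan says.** Section III describes a "prospective, nonrandomized, open-label, single-arm clinical trial". Patients are to "receive sirolimus treatment for at least 6 months", and the only sample-size statement is "No less than 20 patients should be enrolled".

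Section IV.D is the whole rejection rule. Its two grounds are "Patients who violate the requirements of the test protocol" and "Patients with poor-recording, incomplete, or inaccurate data". It does not say how serious a violation or how large a data gap must be, who decides, when, or what rejection does to the analysis.

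Exit is a separate heading, IV.C. Besides allergy, patient request and harm as judged by the investigators, it covers cases where "there is significant issues of compliance, safety, or surgery for venous malformations". Section V.C adds two exits for adults. One is at the lowest dosage: "If patient still cannot tolerate minimum dosage, withdraw from the study". The other follows the month-3 review: "If improvement of disease condition is not obvious, change dosage to 2.5mg-3mg once a day", after which a patient who cannot tolerate the change may leave.

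Section VI.B plans efficacy and safety evaluations at months 3 and 6. Section VI.C plans one at the end of drug therapy and two later.

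Section VIII gives descriptive statistics, 95% intervals and a list of topics (quality of life, lesion size and volume, symptoms, adverse events). It contains no analysis set, no denominator and no rule for missing data.

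**The concern.** Protocol violations and incomplete records arise mainly after enrolment, so IV.D reads naturally as removing patients who have already been treated. Nothing in section VIII puts them back.

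Without a control arm, the efficacy result is the change from baseline in whoever is analysed. A comparison group would not be there to show that the analysed patients had been selected. Because the trial is open-label, a rejection can be decided by someone who knows how the patient did.

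Both objectives in section II are exposed. For efficacy, a summary of retained patients may differ from what treated patients experienced. For safety, which is the first objective, IV.D leaves open whether a rejected patient also leaves the adverse-event denominator. The plan has no hypothesis test or decision threshold, so the harm is a misleading estimate and not a wrong test decision.

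**Working it through.** **Link from exit to rejection, read from the text**

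1. A patient exits early under IV.C or V.C. This is stated.
2. That patient can lack later evaluations under VI.B. This follows from the schedule.
3. Missing evaluations can count as incomplete data under IV.D. This is a possible reading of an undefined word.
4. Rejection removes the patient from the summaries. IV.D does not say so, and section VIII does not prevent it.

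The routes tied to outcome are safety, intolerance and venous-malformation surgery. No listed route removes patients because they improved. Patient request and compliance are neutral on their face.

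**Inputs**

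- N = 20, the minimum in section III. The documents give no derivation, so it cannot be reproduced and is used as given.
- 95% confidence level, from VIII.A.
- Numbers removed (m), numbers improved and differences in SD are all assumed. The documents give no dropout rate, response rate or improvement criterion.

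**Bound that needs no response rate**

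Unknown width of the all-treated rate = 100 × m/N. At N = 20, m = 1, 2, 4 or 6 leaves 5, 10, 20 or 30 points unknown. At an assumed N = 40, m = 2, 4 or 6 leaves 5, 10 or 15.

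**Illustration for a rate, N = 20, with 12 improvers among all treated**

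Exact (Clopper-Pearson) 95% intervals:

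- All treated: 12/20 = 60% (36-81%).
- 2 non-improvers removed: 12/18 = 66.7% (41-87%).
- 4 non-improvers removed: 12/16 = 75% (48-93%).
- 6 non-improvers removed: 12/14 = 85.7% (57-98%).

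With m = 4 and x improvers among those removed, bias = (12 − x)/16 − 12/20:

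| x of 4 improved | Retained only | Bias (points) |
|---|---|---|
| 0 | 12/16 = 75.0% | +15.0 |
| 1 | 11/16 = 68.75% | +8.75 |
| 2 | 10/16 = 62.5% | +2.5 |
| 3 | 9/16 = 56.25% | −3.75 |
| 4 | 8/16 = 50.0% | −10.0 |

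The bias is upward whenever the removed patients improve less often than the 60% of all treated.

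**Illustration for a continuous measure**

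Bias = (m/N) × (mean change in retained − mean change in removed), with larger change meaning more benefit. With m = 4, (4/20) × 0.5 SD = 0.10 SD and (4/20) × 1 SD = 0.20 SD if the removed patients did 0.5 or 1 SD worse. It is zero if they did equally well, and the sign reverses if they did better.

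**Illustration for safety**

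If 4 of 20 leave for an adverse event, the rate is 20% (6-44%). If all 4 are rejected from the denominator as well, the retained set shows 0/16 (0-21%).

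**The case against.** The strongest reply is that the harm is a chain of inferences. Exit and rejection are separate headings, and no sentence makes one lead to the other. This stands: the plan permits a retained-only summary but does not state one. It does not remove the defect, because the rejection rule is written down and nothing in section VIII limits its effect.

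A reader might infer that stopping before 6 months is itself a protocol violation. The documents do not support that. IV.C and V.C expressly allow early exit, so only the incomplete-data ground can reach such patients through the exit itself.

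A reader might also infer that adults who leave at the raised dosage are non-responders, and so treat the 60% figure as what the plan implies. That goes too far. The month-3 review is a dosing judgement and not an analysed endpoint, the step applies to adults only, leaving is optional, and no improvement criterion is given.

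It is fair to add that most listed outcomes are naturally continuous, so a responder rate may never be reported, and that 5 points per patient holds for any trial of 20. Section IX plans unified efficacy criteria and inspections, and section VII requires adverse events to be recorded, followed and reported as incidence. These reduce recording faults and support safety reporting, but they name no denominator. Comparing enrolled with analysed numbers would show that removals occurred, but the plan does not require it and it would not show how the removed patients fared.

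**Conclusion.** The point holds in this limited form. IV.D allows treated patients to be removed with outcomes visible, and section VIII has no set that keeps them in. If patients who leave for safety, intolerance or venous-malformation surgery are rejected, the expected direction is towards overstated benefit and understated harm.

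A reader might conclude that the bias is certain to be upward. The documents do not establish that: rejection for poor records alone could be neutral, and a downward bias is arithmetically possible, although no listed exit route selects for improvers.

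The size is unknown. Only the minimum of 20 and the 95% level come from the documents, and the move from 60% to 75% rests on assumed counts. In a descriptive trial with no decision rule, this is a cheap improvement that should be made, with medium confidence.

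**What to change.** 1. In section VIII, make all patients who took at least one dose the main set for both efficacy and safety.
2. In IV.D, state that rejection does not remove a patient from that set. Use it only for a labelled secondary per-protocol analysis, with criteria fixed before outcomes are reviewed. Query inaccurate values or set them to missing, and keep the patient.
3. For any improvement rate, use the all-treated denominator and count unassessed patients as not improved. For continuous measures, use all available evaluations of treated patients, including the month-3 and end-of-therapy evaluations of early stoppers (VI.B, VI.C). Report the number with data at each visit, and add a sensitivity analysis assuming no change from baseline where data are missing.
4. Report every exit and rejection with its reason and date.
5. Reconcile withdrawal from the study in IV.C and V.C with the end-of-therapy evaluation in VI.C, so that it is clear whether patients who stop early and still consent are evaluated.

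**Cost.** Wording in IV.C, IV.D, V.C and VIII, and a little more analysis. No new type of visit is needed. If the end-of-therapy evaluation is not currently done in early stoppers, it adds the pre-trial examinations for them, including imaging and, where the gut is affected, endoscopy. Counting unassessed patients as not improved is deliberately cautious, so the efficacy figure may be less favourable.

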### **B. Evaluation during sirolimus treatment**

Adverse reactions are evaluated weekly during the first month of drug treatment. The efficacy and safety are then evaluated at the 3rd and 6th months, and the content of the examination is the same as the pre-trial evaluation.

- 1) Efficacy assessment:
  - a. Clinical symptom assessment (including VAS pain score, gastrointestinal bleeding, quality of life (Qol) evaluation, frequency of blood transfusion treatment and other related symptoms);
  - b. Changes in hemoglobin;
  - c. Coagulation I+D-dimer examination;
  - d. Nutritional status (including albumin, etc.);
  - e. Ultrasound, MRI examination of the lesion, abdominal and pelvic cavity contrast-enhanced CT + small intestine reconstruction CT examination, digestive system endoscopy to measure the size, quantity and total load of VM lesions;
- 2) Safety assessment: Safety parameters (such as asking adverse events, measuring laboratory values, vital signs, gastrointestinal bleeding, etc.) will be closely monitored on a regular basis throughout the study.
- 3) Treatment compliance: In order to monitor compliance, subjects are required to complete an electronic diary during the entire study period. Dates of drug intake will be tracked by this diary. At every visit, the investigator and the subject will review the electronic diary data together.

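### Rejecting patients for incomplete data, with no exemption for withdrawals, can drop adults without obvious month-3 improvement and may bias the single-arm efficacy summary upward

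*Combined protocol and SAP*

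**What the plan says.** Section IV.D (Rejection criteria) stands apart from the inclusion, exclusion and exit criteria. Its item (2) rejects "Patients with poor-recording, incomplete, or inaccurate data". It does not define incomplete, does not say which analysis a rejected patient leaves, and makes no exception for withdrawal.

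Section V.C item 2 divides adults by response after three months on 2 mg. Improved adults stay on that dose. Those without obvious improvement go up to 2.5-3 mg. For them the text continues: "If this dosage cannot be tolerated, patients may withdraw from the study". The next sentence is "If it can be tolerated, continue to take for another 3 months and reassess the improvement of condition". The children's regimen in Section V.B has no such step.

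There are other exits. Section V.C item 1 says of adults on 1 mg/day: "If patient still cannot tolerate minimum dosage, withdraw from the study". Section IV.C covers allergy and cases where "there is significant issues of compliance, safety, or surgery for venous malformations", and it allows withdrawal on request: "Subjects may refuse to participate in further studies at any time without providing reasons".

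On timing, Section VI.B says "The efficacy and safety are then evaluated at the 3rd and 6th months". Section VI.C adds an evaluation when drug therapy ends, without saying whether this covers people who stop early. Section VIII.B item 2 lists the efficacy topics but not who is included. Section VIII.A plans descriptive statistics and 95% confidence intervals. On enrolment, Section III says "No less than 20 patients should be enrolled".

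**The concern.** Completeness of trial data can hardly be judged before the trial, so Section IV.D most naturally means removal after enrolment. A patient who stops before month 6 is an obvious candidate for having incomplete data. Combined with Section V.C item 2, this gives an exit open only to adults whose early response was unconvincing, followed by a rule that can delete them.

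With one arm, there is no control group in which the same loss would show. Section IV.D also rejects patients rather than visits. A leaver's month-3 assessment, made before the escalation step opens, could therefore be lost as well, so the month-3 summary is not safe either. Because the study is open-label and the rule is loose, the choice of whom to reject could be made with outcomes already known.

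**Working it through.** **Inputs.** The minimum enrolment of 20 comes from Section III. The plan gives no response rate, dropout rate, effect size or responder definition, so there is no figure of its own to reproduce. All rates below are assumptions.

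**Does the path exist in the text?**
1. A leaver under Section V.C item 2 is an adult, lacks obvious month-3 improvement, has been escalated, does not tolerate the higher dose, and chooses to leave.
2. Only those who tolerate the dose are reassessed after three more months. The leaver has no month-6 value unless the end-of-therapy evaluation in Section VI.C applies, which is not stated.
3. Section IV.D item (2) can then be applied, and nothing in Section VIII prevents it.

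**Direction.** Let d be the share of patients who leave and are rejected, p the month-6 improvement rate in those retained, and q the rate the leavers would have had. The all-patient rate is (1 - d)p + dq, so

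bias = p - [(1 - d)p + dq] = d(p - q).

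The bias is upward only if q < p. With p = 0.60:

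| d | q = 0 | q = 0.20 | q = 0.40 | q = 0.60 | q = 0.80 |
|---|---|---|---|---|---|
| 10% | +6 points | +4 | +2 | 0 | -2 |
| 20% | +12 points | +8 | +4 | 0 | -4 |

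**Worst case in counts (q = 0).** With m of 20 improved and k non-improved leavers dropped, the reported rate is m/(20 - k).

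| m | True rate | k = 1 | k = 2 | k = 3 |
|---|---|---|---|---|
| 8 | 40.0% | 42.1% | 44.4% | 47.1% |
| 10 | 50.0% | 52.6% | 55.6% | 58.8% |
| 12 | 60.0% | 63.2% | 66.7% | 70.6% |

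For m = 10 the excess is 2.6, 5.6 or 8.8 points. With 40 enrolled and 20 improved, the same k gives 20/39 = 51.3%, 20/38 = 52.6% and 20/37 = 54.1%.

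**Continuous measures.** If leavers' mean change is r times that of completers, the completer mean divided by the all-patient mean is 20/(20 - k + kr). For k = 1, 2, 3 this is 1.05, 1.11, 1.18 at r = 0; 1.03, 1.05, 1.08 at r = 0.5; and 1.00 at r = 1.

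**Other exits.** Dropping one improved leaver gives 9/19 = 47.4% against 50.0%, a shift downward.

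**Against sampling error.** The exact (Clopper-Pearson) 95% interval for 10/20 is 27.2% to 72.8%. The shifts are smaller than this, but the interval makes no allowance for them.

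**The case against.** The strongest reply is that the plan never says a withdrawn patient has incomplete data, or that rejection removes anyone from the efficacy summary. Exit and rejection are separate lists, and the wording of Section IV.D item (2) could be about record quality alone. Leavers under Section V.C item 2 do have a month-3 assessment, and the end-of-therapy evaluation can be read as following whenever therapy stops. This stands in part: the link from withdrawal to rejection is the natural reading, not stated text. But nothing excludes that reading, and a sentence would settle it.

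The route is also narrow. It needs several conditions in turn, applies to adults only, and does not forbid a return to 2 mg. The number affected may be zero. That stands, and it limits the expected size.

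The analysis is descriptive, with no test or success threshold. That also stands. The point concerns how favourable the published summary looks, not a false-positive claim.

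A reader might infer that these leavers were failing on treatment. The text says only that improvement was not obvious, which leaves room for modest benefit. A reader might also infer that rejecting leavers always inflates the result. The documents do not support that: exits under Section V.C item 1 and Section IV.C are open to improved patients too, so the net direction over all exits is unknown.

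**Conclusion.** The concern holds in conditional form. As written, Section IV.D item (2) allows patients who leave treatment to be dropped from the efficacy summary, including their recorded month-3 results. For the exit in Section V.C item 2, the bias is upward if three things happen: patients take that exit, they are rejected, and they would have done worse than those retained. The last is plausible given how they were selected, but it is not established.

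The documents do not give the size. At 20 patients with 10 improved and 1 to 3 leavers, the worst case is 2.6 to 8.8 points. It shrinks as the leavers' prospects approach those of the others and reaches zero when they are equal, when nobody leaves, or when all leavers are kept. The plan should be changed because the remedy is cheap and a single arm cannot reveal the problem afterwards. It would go too far to say that the trial's result is biased.

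**What to change.** 1. **Sections IV.D item (2) and VIII.B item 2.** State that a patient who received sirolimus is not rejected because withdrawal left the data incomplete. Make all treated patients the main efficacy population, with completers shown beside it. Section IV.D item (1) and the rule on inaccurate data need not change.
2. **Any improved/not-improved summary.** Count as not improved those who leave before month 6 for intolerance, lack of benefit, allergy, safety or VM surgery, and those with no on-treatment efficacy assessment. Report other leavers by number, reason and last on-treatment judgement.
3. **Continuous measures.** Report month-3 values for all treated patients assessed, and month-6 values with the number missing and the reasons. A last-value summary is optional, as a sensitivity analysis only, since it assumes no change after stopping.
4. **Section VI.C.** State that the end-of-therapy evaluation applies to early leavers who agree. Limit it to symptoms, quality of life and laboratory tests unless imaging or endoscopy is clinically due. The full pre-trial content includes MRI and, for gastrointestinal disease, contrast CT and endoscopy, which is a heavy burden for someone leaving.

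**Cost.** A few sentences, no extra patients, and one limited visit for each consenting leaver. The reported improvement rate may be lower and somewhat conservative. At 20 patients, each leaver counted as not improved who would have improved lowers it by 1/20 = 5 points. The completer summary alongside lets readers see the difference.

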## **V. Therapeutic schedule**

### **A. Enrollment**

Before starting the study, the investigator clearly and colloquially explains the study and its potential risks and benefits to the patient or his/her authorizer. Patient or his/her authorized and the investigator sign and date the informed consent form. Only after signing the informed consent form can patient or his/her authorizer enter the screening section. Patients who sign a written informed consent need to be assessed to determine if the patient meets the study criteria:

- 1) Demographic data and medical history of the patient;
- 2) vital signs;

### **B. Children's dosage regimen**

Oral administration

The initial dose of oral rapamycin intake is 1 mg/m^2 of body surface area. Drug trough concentration in patient's blood is maintained at 5-10 ng/ml.

### **C. Adults' dosage regimen**

Oral administration

1) Initial dose and dosing schedule: sirolimus 2mg, once a day. Maintain drug trough concentration of 5-10ng / mL in blood. If adverse events are too severe to tolerate, daily dosage can be reduced by 0.5mg every week. The minimum dosage is 1 mg/day. If patient still cannot tolerate minimum dosage, withdraw from the study. If patient could tolerate the possible adverse events, continue to take the original dose for 3 months, and evaluate improvement of disease condition.

2) Subsequent dose and dosing schedule: After taking sirolimus 2 mg once a day for 3 months, those with improved condition continue to take the original dose. If improvement of disease condition is not obvious, change dosage to 2.5mg-3mg once a day. If this dosage cannot be tolerated, patients may withdraw from the study. If it can be tolerated, continue to take for another 3 months and reassess the improvement of condition.

3) Blood drug concentration test: Blood samples are taken at 1st, 3rd and 6th months of dosage schedule.

4) Iron supplementation: For subjects with hemoglobin  $\leq$  10.9 g / dl, iron supplementation should be provided according to the standard dosing regimen, but iron supplementation is

not considered as study treatment and will be recorded as concomitant medication.

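### Intolerance, significant safety issues and VM surgery end a patient's time in the study, not only on sirolimus, which puts later safety and efficacy data at risk

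*Combined protocol and SAP*

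**What the plan says.** The exit rules are in two places.

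- **V.C Adults' dosage regimen.** The dose may be lowered in weekly 0.5 mg steps to a floor of 1 mg/day. At that floor: "If patient still cannot tolerate minimum dosage, withdraw from the study". After escalation to 2.5–3 mg the rule is only permissive: "If this dosage cannot be tolerated, patients may withdraw from the study".
- **IV.C Exit criteria.** Item (1) is "An allergic reaction occurs". Item (3) is mandatory: "Subjects are required to withdraw from the study in certain special circumstances", with the examples "significant issues of compliance, safety, or surgery for venous malformations". Item (4) covers situations in which the study has to stop, for example where "the investigators believe that continuing the study may be harmful to the health of subjects". Item (2) is withdrawal at the patient's request.

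Four other sections bear on what happens next.

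- **VI.B**, headed "Evaluation during sirolimus treatment", has weekly adverse-reaction checks in month 1, then efficacy and safety evaluations at months 3 and 6.
- **VI.C** adds evaluations when drug therapy ends and 6 and 12 months later, with the same content as the baseline work-up. It does not mention patients who stop early.
- **VII.E.4** follows every adverse event to resolution and abnormal laboratory values back to baseline.
- **IV.D Rejection criteria** lists "Patients with poor-recording, incomplete, or inaccurate data".

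Section VII.C, on grading, speaks of withdrawing the medication for severe reactions. The protocol therefore has the idea of stopping the drug, but the exit rules do not use it.

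**The concern.** Safety is the first objective listed in section II and efficacy the second. Patients who cannot tolerate the lowest dose, have a significant safety problem or come to VM surgery are informative for both. If they leave the study when they leave the drug, observation ends for reasons tied to outcome. Month-3, month-6 and later summaries would then describe mainly patients who tolerated sirolimus and needed no VM surgery. With a single arm, no comparison group is selected in the same way to offset this. Section VIII has no rule for patients without a later evaluation, so nothing in the analysis would restore them.

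Three kinds of data are at risk: adverse events that begin after exit, scheduled checks still to come, and efficacy measurements.

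**Working it through.** The plan states no exit rate, dropout allowance or response rate, so there is no figure of its own to reproduce. The check has three parts.

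**1. Can an intolerant adult exit before month 3?**

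Inputs from V.C: starting dose 2 mg, floor 1 mg, step 0.5 mg per week.

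- Number of reductions: (2 − 1)/0.5 = 2.
- With the first reduction at the end of week w, the second comes at w + 1. Assuming one week at 1 mg, exit is at w + 2.
- Month 3 is about week 26/2 = 13. With w = 10, exit is at week 12.

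So an adult whose first reduction comes by week 10 can be out before any efficacy evaluation has taken place.

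**2. How many evaluations does an early stopper miss?**

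VI.B schedules 2 (months 3 and 6). VI.C schedules 3 (end of therapy, +6 and +12 months). On paper this is 2 + 3 = 5. Section III plans at least 6 months of treatment. If treatment lasts exactly 6 months, month 6 and end of therapy coincide, leaving 5 − 1 = 4 distinct evaluations.

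| Exit | Missed if VI.C applies from the last dose | Missed if study withdrawal overrides VI.C |
|---|---|---|
| Before month 3 | 2; only 1 if a VI.C visit falls close enough to serve (exit at week 12 puts end of therapy one week from month 3) | 2 + 3 = 5 on paper, or 4 distinct |
| Between months 3 and 6 | 1; none if end of therapy coincides with month 6 | 1 + 3 = 4 on paper, or 3 distinct |

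The range is wide because the text does not say which column applies.

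**3. What is one exit worth?**

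Section III sets a minimum of 20 patients, so one patient is 1/20 = 5 percentage points of a proportion. If k of 20 have no month-6 evaluation, the proportion improved among all 20 is known only to within k/20: 5 points for one, 10 for two, 20 for four.

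For illustration, assume about 80% improvement among those evaluated. Both this figure and the numbers of exits are assumptions. Intervals are exact 95% (Clopper–Pearson).

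| Assumed exits | Evaluated patients only | All 20, exits not improved | All 20, exits improved |
|---|---|---|---|
| 2 | 14/18 = 78% (52–94%) | 14/20 = 70% (46–88%) | 16/20 = 80% |
| 4 | 13/16 = 81% (54–96%) | 13/20 = 65% (41–85%) | 17/20 = 85% |

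With two assumed exits, the figure for evaluated patients exceeds the one counting exits as not improved by 8 points (78 − 70). With four, the gap is 16 points (81 − 65).

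**The case against.** The strongest reply is that no sentence says visits stop at exit. VI.C is timed from the end of drug therapy, not from completing 6 months, so on its face it fits a patient who stops early. Section III has patients followed on a regular schedule. VII.E.4 covers all adverse events and abnormal laboratory values, not just the event that led to exit. In a single-arm descriptive study it is also defensible to end efficacy evaluation at VM surgery, because lesion size and load afterwards no longer reflect sirolimus alone.

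Much of this stands, and it rules out several stronger readings.

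- A reader might infer that follow-up certainly ends at exit. That is an inference from the exit wording and the heading of VI.B; the documents do not state it.
- A reader might infer that five evaluations are lost. That needs study withdrawal to override VI.C and end of therapy to be distinct from month 6.
- A reader might infer that exited patients are also rejected under IV.D for incomplete data. Exit and rejection are separate lists, and nothing links them.
- A reader might take exit after intolerance of 2.5–3 mg as compulsory. The wording only permits it.
- A reader might infer that follow-up should continue after every kind of exit. IV.C(4) covers cases where the study itself must stop or may do harm, so a blanket rule would not fit there.

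One further point is fair: collecting off-drug data and reporting them only separately would leave the on-drug summary just as selected. The remedy therefore needs a denominator rule as well.

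The reply does not remove the gap. For three outcome-related reasons the protocol orders withdrawal from the study, and no provision keeps the remaining month-3 and month-6 evaluations for these patients.

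**Conclusion.** The concern holds as a fault in a stated rule. Intolerance of 1 mg/day, significant safety issues and VM surgery lead to withdrawal from the study where stopping sirolimus would do. Read literally, remaining month-3 and month-6 evaluations fall away, and the status of the VI.C evaluations is unclear. Existing adverse events and abnormal laboratory values remain protected by VII.E.4.

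Per patient, the loss runs from no distinct evaluation to all those remaining, depending on how VI.C is read and when exit occurs. For the trial as a whole, the size of any bias cannot be derived, because neither an exit rate nor a late-event rate is given. Selection towards patients who did well is likely, since the exit reasons are tied to outcome. The 5 points per patient is one patient's weight at minimum enrolment, not an estimated effect.

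The conclusion rests on taking the exit wording literally. It deserves a change because the remedy is cheap and uses visits already planned.

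**What to change.** - **IV.C(1), IV.C(3) and V.C.** For allergy, intolerance, safety issues and VM surgery, replace study withdrawal with stopping sirolimus and remaining in follow-up. Stating this in IV.C also covers children, since V.B has no intolerance rule. The exceptions are withdrawn consent (IV.C(2)) and an investigator's judgement that follow-up itself would be harmful (IV.C(4), left as written). When the drug is stopped does not change.
- **VI.B and VI.C.** State that VI.C applies to early stoppers, counted from the last dose. Keep any remaining month-3 and month-6 symptom, laboratory and adverse-event assessments. Let one visit serve both schedules when they fall close together. Do endoscopy and contrast CT only where clinically suitable.
- **IV.D.** State that stopping early is not a ground for rejection.
- **VIII.** Report safety for all treated patients. Report month-3 and month-6 efficacy proportions with all treated patients in the denominator, counting those who stopped for intolerance, safety or VM surgery as not improved on sirolimus. Show off-drug and post-surgery values labelled as such.

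The cost is the effort and expense of retaining a few off-drug patients, and possibly a less favourable response figure. Section XI says only that the drug is free, so the amendment should also state who pays for the off-drug checks.
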